8.4 Data Safety Monitoring Committee

A Data Safety Monitoring Committee (DSMC) at HCI is charged with ensuring the risk/benefit balance for subjects undergoing study therapy. The purpose of the DSMC is to ensure subject safety and make recommendations for study conduct to ensure subject safety and data integrity. The DSMC is chaired by a medical oncologist and may include, but is not limited to, representatives from medical oncology, oncological sciences, biostatistics, and pharmacy.

The roles and responsibilities of the DSMC are described in the NCI-approved Data and Safety Monitoring (DSM) plan. The activities of the committee include reviewing adverse events (including SAEs), deviations, important medical events, and approving cohort/dose escalations. Amendments that increase risk, increase treatment exposure, or impact study objectives will also be reviewed by the DSMC. If the DSMC and/or the PI have concerns about unexpected safety issues or AE trends, the study may be stopped and an unplanned safety data analysis may be conducted. Enrollment will not resume until the issues are resolved. The DSMC also reviews and approves audit reports generated by the Research Compliance Office.

All trials will be assigned an oncologist member of the DSMC to serve as a medical monitor. In rare cases, an external medical monitor may be assigned. The Medical Monitor will be notified of all serious adverse events (SAEs). Specific notifications will also be issued when a dose-limiting toxicity is encountered and when the RP2D is defined. Approval from the Medical Monitor is required for all dose escalations. All serious adverse events (SAEs) occurring in subjects treated at HCI or its affiliates will also be reviewed by the full DSMC monthly.

Each trial is assigned a research compliance officer who will be responsible for monitoring the trial and reporting to the DSMC. The assessed risk level of the trial will determine the frequency with which monitoring occurs. The Research Compliance Officer monitor will review the study status and summarize enrollment, toxicities, SAEs, dose-escalation, statistical endpoints (e.g., stopping rules), deviations, and any other pertinent information for the full DSMC membership at the regularly scheduled meetings.

Audits will be conducted for all trials one year after enrollment begins and annually thereafter. Audits may be conducted more frequently as requested by the DSMC, Institutional Review Board (IRB), Protocol Review and Monitoring Committee (PRMC), Research Compliance Office management, or the Principal Investigator.

DSMC oversite will be tailored to the assessed risk level of the trial. Trials are categorized amongst three risk levels: high, moderate, and low.

This trial has been classified as high risk and therefore will be monitored by RCO and reviewed by DSMC after the first subject is enrolled and then quarterly thereafter.

9 STATISTICAL CONSIDERATIONS

9.1 Sample size determination

Assuming a parametric exponential survival model, with a minimum 12-month follow-up and a 10% significance level (1-sided), 21 patients will achieve an 90% power for PFS analysis, assuming a null hypothesis median survival of 1.7 months and an alternative hypothesis median survival of 4 months. The null hypothesis is based on the literature for median progression free survival noted in multiple randomized phase III trials who received no additional therapy. The sample size estimation for this and alternative designs are summarized in the following Table 4. (see the line below shaded in Table 4).

Table 5: Statistical Plan

Numeric Results

Test Based on Theta-hat with Fixed Running Time t0 and Without Replacement Sampling.

H0: Theta = Theta0. Ha: Theta = Theta1 < Theta0. Reject H0 if Theta-hat ≤ ThetaC.

Power	N	t0	Time		Target Alpha	Actual Alpha	Target Beta	Actual Beta	Theta C
			Theta0	Theta1					
0.80684	21	12.000	0.4	0.2	0.05000	0.05000	0.20000	0.19316	0.3
0.90532	28	12.000	0.4	0.2	0.05000	0.05000	0.10000	0.09468	0.3
0.80420	15	12.000	0.4	0.2	0.10000	0.10000	0.20000	0.19580	0.3
0.90396	21	12.000	0.4	0.2	0.10000	0.10000	0.10000	0.09604	0.3

References

Bain, L.J. and Engelhardt, M. 1991. Statistical Analysis of Reliability and Life-Testing Models. Marcel Dekker. New York.
 Epstein, Benjamin. 1960. 'Statistical Life Test Acceptance Procedures.' *Technometrics*. Volume 2.4, pages 435-446.
 Juran, J.M. 1979. Quality Control Handbook. McGraw-Hill. New York.
 Schilling, Edward. 1982. Acceptance Sampling in Quality Control. Marcel-Dekker. New York.

Report Definitions

Power is the probability of rejecting a false null hypothesis.

N is the size of the sample drawn from the population.

Alpha is the probability of rejecting a true null hypothesis.

Beta is the probability of accepting a false null hypothesis.

Theta0 is the Mean Life under the null hypothesis.

Theta1 is the Mean Life under the alternative hypothesis.

t0 is the test duration time. It provides the scale for Theta0 and Theta1.

r is the number of failures.

Summary:

A sample size of 21 achieves 90% power to detect the difference between the null hypothesis mean lifetime of 0.4 and the alternative hypothesis mean lifetime of 0.2 at a 0.10000 significance level (alpha) using a one-sided test based on the elapsed time. Failing items are not replaced with new items. The study is terminated when it has run for 12.000 time units.

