5.6.1 Number of Subjects

Up to 25 patients to get 21 evaluable patients for efficacy as defined in Section 9.2.2.

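### Section 9.1 pairs 21 patients and 90% power with a 4-month alternative median PFS, but the sample-size table's own power values imply about 3.0 months

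*Combined protocol and SAP*

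**What the plan says.** Section 9.1 sets the size of the trial for its primary endpoint, PFS. The model is "Assuming a parametric exponential survival model", with a one-sided significance level of 10% and at least 12 months of follow-up. The claim is that "21 patients will achieve an 90% power for PFS analysis". The effect to which this claim is tied is expressed in medians: "assuming a null hypothesis median survival of 1.7 months and an alternative hypothesis median survival of 4 months".

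The supporting software output follows as Table 5 (the text calls it Table 4). It has four rows: two values of alpha crossed with two power targets. The parameter Theta is defined as mean life and printed to one decimal, with 0.4 under the null and 0.2 under the alternative in every row. The rule is "Reject H0 if Theta-hat ≤ ThetaC", and the test duration is 12 time units. The summary beneath repeats the 90% power for 21 patients with a "null hypothesis mean lifetime of 0.4 and the alternative hypothesis mean lifetime of 0.2".

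Section 5.6.1 carries the number forward: "Up to 25 patients to get 21 evaluable patients for efficacy as defined in Section 9.2.2".

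**The concern.** The text works in median months (1.7 and 4). The table works in a parameter called mean life (0.4 and 0.2). Under an exponential model a 1.7-month median has a mean of 1.7/ln 2 = 2.45 months and a 4-month median a mean of 5.77 months, so 0.4 and 0.2 cannot be mean lives in months. They do look like monthly hazards: ln 2/1.7 = 0.408 and ln 2/4 = 0.173. At one decimal, however, 0.173 cannot be told apart from ln 2/3 = 0.231, because both print as 0.2. The printed inputs therefore do not show which alternative was used, but the printed powers can.

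The alternative median is the plan's only statement of the effect sought. If the sample size was worked out for a smaller effect, readers and the IRB are told that the trial targets 4 months when it was sized to detect a clearly shorter median.

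**Working it through.** **Inputs, all from Section 9.1.** Exponential PFS; one-sided alpha; medians 1.7 and 4 months; and the four table rows: N = 21, alpha 0.05, power 0.80684; N = 28, alpha 0.05, power 0.90532; N = 15, alpha 0.10, power 0.80420; N = 21, alpha 0.10, power 0.90396.

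**Formula.** With a test duration of 12 and Theta near 0.4, the chance of no event is exp(−12/0.408), about 1e−13, so the table treats every failure as observed. Its lower-tail test then has

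power = P(χ²₂ₙ ≤ R × q), where R = Theta0/Theta1 and q is the alpha quantile of χ² with 2N degrees of freedom.

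Power depends on the two parameters only through R.

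**Step 1: what ratio do the printed powers imply?** Solving each row for R gives 1.76623, 1.76624, 1.76624 and 1.76623. Three sample sizes and two alphas agree on one ratio. With the null at 1.7 months the alternative is 1.7 × 1.7662 = 3.00 months. The stated medians need R = 4/1.7 = 2.353.

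**Step 2: reproduce the table.** Take Theta0 = 0.408 (ln 2/1.7) and Theta1 = 0.231 (ln 2/3.0), so R = 1.76623. For N = 21 and alpha 0.10, q = 30.765 on 42 degrees of freedom, R × q = 54.339, and P(χ²₄₂ ≤ 54.339) = 0.90396, as printed.

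| N | alpha | printed power | 0.408 vs 0.231 (1.7 vs 3.0 months) | 1.7 vs 4 months | 0.4 vs 0.2 taken literally |
|---|---|---|---|---|---|
| 21 | 0.05 | 0.80684 | 0.80684 | 0.990 | 0.931 |
| 28 | 0.05 | 0.90532 | 0.90532 | 0.999 | 0.979 |
| 15 | 0.10 | 0.80420 | 0.80420 | 0.982 | 0.916 |
| 21 | 0.10 | 0.90396 | 0.90396 | 0.998 | 0.974 |

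The critical value in the last row is 0.408 × 30.765/42 = 0.299, which agrees with the printed 0.3. Of all three-decimal pairs that round to 0.4 and 0.2, only 0.408 and 0.231 match all four rows to five decimals.

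**Step 3: could rounding hide 4 months?** No. If Theta0 lies between 0.35 and 0.45 and R = 1.766, Theta1 is at least 0.35/1.766 = 0.198; to print as 0.2 it must also be below 0.25. Those hazards correspond to medians of ln 2/0.25 = 2.8 to ln 2/0.198 = 3.5 months.

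**Step 4: could another test give 90% at 4 months?** With N = 21 and 1.7 vs 4 months:

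- table's lower-tail test, alpha 0.10: 0.9975
- upper-tail test on the mean (the natural test for longer PFS), alpha 0.10: 0.9925
- normal approximation for the log ratio, alpha 0.10: 0.996
- simulation with censoring at 12 months, alpha 0.10: 0.992
- alpha 0.05 instead, across these tests: 0.983 to 0.990

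None is near 0.90. At 3.0 months the upper-tail test gives 0.903 and the censored simulation 0.900.

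**Step 5: what would 90% at 4 months need?** Ten patients give 0.9135 (upper tail) or 0.9175 (lower tail); nine give 0.89. Conversely, with 21 patients 90% power is reached at a median of 2.99 months.

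**The case against.** The strongest reply is that the error is on the safe side. If 4 months is the real target, 21 patients are more than enough; the sample size, alpha and null all stand, and Section 5.6.1 is consistent with either alternative. This is correct and limits the consequence, but it does not make the sentence true.

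Second, 3.0 months is nowhere printed. The powers fix only a ratio, and reaching 3.0 months means holding the null at 1.7 and reading Theta as a monthly hazard, against the table's own label. That is fair: 3.0 is an inference, though a tight one. The exclusion of 4 months needs no such reading, because a ratio of 2.353 does not give the printed powers whatever Theta is called.

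Three limits on side figures also stand.

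- **Rejection boundary.** It depends on the test: an estimated median of about 2.2 months for the test on the mean (1.7 × 54.090/42 = 2.19, or 2.20 with censoring), and about 2.32 months under the table's rule (ln 2/0.299). Section 9.3 names no PFS test, so neither is a declared rule.
- **Ten patients.** This figure assumes exactly observed exponential times. Scans are every 8 weeks, longer than the null median of about 7.4 weeks, so it shows the size of the mismatch and is not a usable sample size.
- **Alpha.** A one-sided 10% level is a legitimate stated choice. Tightening it would be an option, not a correction.

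**Conclusion.** The point holds. The combination of 21 patients, one-sided alpha 0.10 and 90% power belongs to a comparison of 1.7 with about 3.0 months, not 1.7 with 4 months. For 4 months the power is about 99% (0.992 to 0.998, depending on the test and on censoring).

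This rests on the plan's exponential model and on the printed power values. The 3.0-month figure also needs the stated 1.7-month null and the hazard reading of Theta. The mean-life label is a second error in the same table. The trial is not underpowered for 4 months, but a positive test would not show a 4-month median, since the null is rejected at an estimated median of only about 2.2 to 2.3 months. Because this is the only power statement and the only statement of the effect sought, it needs correcting.

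**What to change.** Restate Section 9.1 in one of two ways.

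1. Give the alternative median as 3.0 months (hazards 0.408 and 0.231 per month) and keep 21 patients with 90% power.
2. Keep 4 months, rerun the table for 1.7 vs 4 months, and state power of about 99% at one-sided alpha 0.10 with 21 patients.

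Under either, print Theta to three decimals and correct its name in the definitions and the summary: hazards if 0.408 and 0.231 are kept, or true mean lives in months with the rejection direction reversed. State which test on PFS will be used, so that the boundary is fixed.

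If 4 months is kept, the sponsor may consider a stricter alpha with the same 21 patients. Using the test on the mean with all events observed, power would be 98.5% at one-sided 0.05 and 97.3% at 0.025. With censoring at 12 months these become about 98.3% and 96.9%.

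The cost is a protocol wording change with no additional patients. The stated detectable effect or the stated power will change.

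### Table 5 enters monthly hazards as mean lifetimes, so the plan's only PFS rejection rule runs the wrong way, and reading it on the hazard scale does not give the stated 10% alpha

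*Combined protocol and SAP*

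**What the plan says.** Section 9.1 assumes exponential PFS, at least 12 months of follow-up and a one-sided 10% test. It claims that "21 patients will achieve an 90% power for PFS analysis". The two hypotheses are set out as medians: "assuming a null hypothesis median survival of 1.7 months and an alternative hypothesis median survival of 4 months".

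The software output in Table 5 states the test: "H0: Theta = Theta0. Ha: Theta = Theta1 < Theta0. Reject H0 if Theta-hat ≤ ThetaC". Its report definitions say "Theta0 is the Mean Life under the null hypothesis" and "Theta1 is the Mean Life under the alternative hypothesis". The summary below the table repeats the scale: "null hypothesis mean lifetime of 0.4 and the alternative hypothesis mean lifetime of 0.2 at a 0.10000 significance level".

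The row matching the text has N = 21, t0 = 12, alpha 0.10000, power 0.90396 and ThetaC 0.3. ThetaC is printed as 0.3 in all four rows.

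Section 9.3 defines PFS but names no test, estimator or threshold. Section 9.4 names Kaplan-Meier for OS only. Table 5 is therefore the only place where a PFS decision rule appears.

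**The concern.** Under an exponential model the mean is the median divided by ln2, so medians of 1.7 and 4 months are means of 2.45 and 5.77 months. Table 5's mean lifetimes of 0.4 and 0.2 match neither. They look like hazards per month, and the alternative lies below the null, which on a mean-life scale is a shorter PFS.

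The trial has one arm and one primary test. If the direction, scale and value of its threshold are not settled beforehand, the rule has to be chosen when the data are in hand.

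**Working it through.** **Inputs.** From Section 9.1: N = 21, one-sided alpha 0.10, medians 1.7 and 4 months, t0 = 12, ThetaC 0.3 (one decimal). Hazards are ln2/1.7 = 0.408 and ln2/4 = 0.173 per month.

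**1. Reproducing Table 5.** If all N patients have events, 2N × Theta-hat / Theta follows chi-square on 2N degrees of freedom. The lower-tail mean-life test has ThetaC = Theta0 × chi2(alpha, 2N)/(2N) and power = P[chi2(2N) ≤ (Theta0/Theta1) × chi2(alpha, 2N)]. With Theta0 = 0.408 and Theta1 = 0.231 (ratio 1.766):

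| N | alpha | chi2(alpha, 2N) | unrounded ThetaC | power | printed power |
|---|---|---|---|---|---|
| 21 | 0.05 | 28.144 | 0.2734 | 0.80684 | 0.80684 |
| 28 | 0.05 | 39.801 | 0.2900 | 0.90532 | 0.90532 |
| 15 | 0.10 | 20.599 | 0.2801 | 0.80420 | 0.80420 |
| 21 | 0.10 | 30.765 | 0.2989 | 0.90396 | 0.90396 |

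All four rows match to five decimals. The stated medians (ratio 4/1.7) give 0.990, 0.999, 0.982 and 0.998. The rounded 0.4/0.2 gives 0.931, 0.979, 0.916 and 0.974. Upper-tail tests need a different ratio in each row. So hazards went into a lower-tail mean-life test. The alternative hazard 0.231 is ln2/3, a 3-month median; the documents do not state that value, and it is inferred from the match.

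**2. The rule as defined (mean life in months).** P(Theta-hat ≤ 0.3) = P[chi2(42) ≤ 42 × 0.3/mean].
- Median 1.7: 42 × 0.3/2.4526 = 5.14, probability 7e-13.
- Median 4: 42 × 0.3/5.7708 = 2.18, probability 4e-20.

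The rule practically never rejects, and rejects less often the longer PFS is.

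**3. The rule read as a hazard.** The estimate is now events/total time, the reciprocal of the statistic the software modelled. Rejecting when it is ≤ C gives alpha = P[chi2(42) ≥ 42 × lambda0/C].
- lambda0 = 0.408, C = 0.2989: P[chi2(42) ≥ 57.33] = 0.058.
- lambda0 = 0.408, C = 0.3: P[chi2(42) ≥ 57.12] = 0.060.
- lambda0 = 0.4: 0.070 at C = 0.2989 and 0.073 at C = 0.3.
- With follow-up capped at 12 months (simulation, lambda0 = ln2/1.7): 0.061 and 0.063.

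Power replaces lambda0 by the alternative hazard. At a 4-month median and C = 0.3, P[chi2(42) ≥ 24.26] = 0.987. At the 3-month median implied by the software input it is 0.855 to 0.858 for the two cuts.

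**4. A correctly directed 10% test.** The cut is Theta0 × chi2(0.90, 42)/42 = 2.4526 × 54.090/42 = 3.159 months, equivalent to an estimated median of 2.19 months or a hazard of 0.317. Power is P[chi2(42) ≥ 54.090 × 1.7/4 = 22.99] = 0.993 at 4 months and P[chi2(42) ≥ 54.090 × 1.7/3 = 30.65] = 0.903 at 3 months. With a 12-month cap, simulation puts the 10% cut at 3.171 months (estimated median 2.20), with power of about 99% and 90%.

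**The case against.** **The inverted reading will not be used.** The opening sentence of Section 9.1 makes the direction plain, and no analyst would claim success at a mean PFS of 0.3 months. A reader might infer that the trial is bound to fail, or would reward harm; the section read as a whole does not support that. What stands is that the written rule contradicts the text and nothing elsewhere replaces it.

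**The 6% is not a property of the printed 0.3.** This is right. ThetaC is shown to one decimal, and the correct hazard cut of 0.317 would also print as 0.3. Values from 0.25 to 0.35 span alpha from 0.6% to 21%. The 6% needs the back-solved cut, or 0.3 taken as exact. The repeated 0.3 across rows is likewise display rounding (0.273 to 0.299), not a separate error.

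**The error is favourable.** On the hazard scale alpha is below 10% and power at 4 months is above 90%. A reader might infer an underpowered trial from the 85–86% figure, but that applies only to an inferred 3-month alternative. The two cuts disagree only for estimated medians from 2.19 (ln2/0.317) to about 2.3 months (ln2/0.3 = 2.31), a gap of about 0.12 months.

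**A replacement cut is fragile.** This stands in part. Section 5.6.1 allows up to 25 patients, but in order to obtain 21 evaluable, so N = 21 is the right basis. Event times are a real limit. Section 7.3.1 schedules scans every 8 weeks, about 1.84 months, which is longer than the null median. If every event under an exponential 1.7-month null were recorded only at the next scan, the mean recorded time would be 1.84/(1 − exp(−0.408 × 1.84)) = 3.49 months, already above the cut. That is an extreme assumption, since deaths, clinical progression and unscheduled scans fall between visits, but the cut must carry the caveat.

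**Conclusion.** The point holds. Table 5 puts monthly hazards into a mean-life test, so the plan's only PFS rejection rule is inverted as written. Taking Theta as a hazard does not rescue it: one-sided alpha is about 6% (7% with the rounded null) instead of 10%, and the printed 90.4% power does not belong to the 4-month alternative in the text.

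The hazard-scale figures assume exponential PFS, 21 patients, exact event times and the back-solved cut of 0.2989 or an exact 0.3. The error on that scale is conservative, with power of about 98.7% at 4 months, so it gives no reason to call 21 patients too few. The defect is that the decision rule is wrong as defined and ambiguous otherwise.

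**What to change.** Rerun Table 5 with Theta as mean PFS in months: null 1.7/ln2 = 2.45, alternative 4/ln2 = 5.77, and Ha: Theta1 > Theta0. If a 3-month alternative was intended, say so and make text and table agree.

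Replace the rule with: reject H0 if total PFS time divided by the number of PFS events is at least Theta0 × chi2(0.90, 2r)/(2r), where r is the number of PFS events. For 21 evaluable patients this is about 3.16 months if all have events, or 3.17 with a 12-month cap. The chi-square form is approximate when follow-up is capped.

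Print the cut to enough decimals to identify it and restate alpha and power from that rule. Say that the cut will be recomputed for the number analysed and the actual follow-up. State that it assumes exact exponential event times, which 8-weekly scans only approximate.

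The cost is one table and two sentences in Section 9.1, with no extra patients.

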9.2 Population for Analyses

9.2.1 Evaluable for toxicity

Study participants who have received at least one treatment with cetuximab infusion will be evaluable for toxicity.

9.2.2 Evaluable for Efficacy

Study participants who have received at least 2 doses of cetuximab and have had one set of restaging CT scans or documented clinical progression will be evaluable for efficacy

All study participants who have received one dose of cetuximab will be included in safety data sets.

Study participants who fail to receive at least 2 doses of cetuximab and have at least one set of CT scans or documented clinical progression will be replaced to ensure 21 response evaluable patients.

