2 OBJECTIVES AND ENDPOINTS

2.1 Primary Objective

To evaluate the progression free survival (PFS) among patients treated with cetuximab in APC, TP53 and RAS mutated refractory metastatic colorectal cancer.

Primary Endpoint: The primary endpoint is progression free survival (PFS). PFS will be measured from the date of first dose of study drug until first documented radiographic evidence of disease progression by RECIST criteria 1.1, clinical progression per investigator judgement, start of new anti-cancer therapy, or death from any cause.

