7.3 Efficacy Assessments

7.3.1 Disease Assessment

Disease assessments must include all known or suspected sites of disease; therefore, the decision for body areas to be scanned will depend on the extent of disease. The minimum recommended body areas to be scanned is chest, abdomen, and pelvis. Response will be defined by RECIST 1.1 (Appendix 3).

Disease assessments will be evaluated radiologically and conducted at baseline (within 28 days before the first dose of study treatment) and then every 8 weeks thereafter regardless of dose holds or delays. Disease assessments will continue until disease progression. Subjects who discontinue treatment for reasons other than progression will continue to have disease assessments until documented clinical or radiographic progression or initiation of subsequent therapy. In addition, radiological tumor assessments will be conducted whenever disease progression is suspected (e.g. symptomatic deterioration) or when clinically indicated. The schedule of tumor assessments should be fixed according to the calendar, starting with cycle one day one, regardless of treatment delays or interruptions due to toxicity.

Brain CT or MRI scans are required at baseline for all subjects with stable brain lesions and for those for whom Central Nervous System (CNS) involvement is suspected. If stable brain metastases are present at baseline, brain imaging should be repeated at each tumor assessment. Otherwise, brain imaging will be conducted post-baseline only when clinically indicated.

The CT and MRI scans should be performed with contrast agents unless contraindicated for medical reasons. Consistent imaging modality should be used for all disease assessments.

7.3.1.1 *Photography of Cutaneous Lesions*

Cutaneous lesions not evaluable by CT or MRI will be documented by color digital photography, including a ruler to estimate lesion size. Photographs must be taken in a manner that protects subject identity and confidentiality (e.g. covering eyes or defining marks or characteristics). Cutaneous lesions may be considered target lesions if they meet RECIST v1.1 criteria, otherwise they may be considered non-target lesions. Photographs of cutaneous lesions will be taken at screening and on the same day as a tumor assessment visit, or at the first clinic visit following each tumor assessment

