9.3 Primary Endpoint

The progression free survival (PFS) is the primary endpoint. PFS will be measured from study entry until first documented radiographic disease progression by RECIST criteria 1.1, clinical progression per investigator judgement, start of new anti-cancer therapy, or death from any cause.

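### No analysis set is named for the primary PFS test, and the implied efficacy-evaluable set would drop and replace some early failures because of their outcome

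*Combined protocol and SAP*

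**What the plan says.** Section 9.3 defines the endpoint ("PFS will be measured from study entry until first documented radiographic disease progression by RECIST criteria 1.1", followed by the other event types) but names no analysis set, test or estimator. Section 2.1 starts the clock at the first dose instead of study entry. It also counts "start of new anti-cancer therapy, or death from any cause" as PFS events.

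The only efficacy set is in Section 9.2.2: "Study participants who have received at least 2 doses of cetuximab and have had one set of restaging CT scans or documented clinical progression". Those who fall short "will be replaced to ensure 21 response evaluable patients". Section 5.6.1 sets enrolment accordingly: "Up to 25 patients to get 21 evaluable patients for efficacy as defined in Section 9.2.2". Section 9.1 uses the same number for the primary test: "21 patients will achieve an 90% power for PFS analysis". Section 9.2.1 defines a set of all patients with at least one infusion, but for toxicity only. Section 9.4 names no set for OS.

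**The concern.** The matching figure of 21 makes the Section 9.2.2 set the implied set for primary PFS, although no sentence says so. Entry to that set depends partly on what happens after treatment starts. A patient who dies after one dose without documented clinical progression is a PFS event under Section 2.1, but is not evaluable and is replaced.

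How many such patients there are depends on the unbracketed 'and/or' in Section 9.2.2:

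- **Strict reading:** two doses are always required. Every failure before the second dose is lost. So are later deaths or new therapy with neither a scan nor documented clinical progression.
- **Lenient reading:** documented clinical progression is enough on its own. The patients lost are those who fail without it and without two doses plus a scan.

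Dropping short PFS times and replacing them with new patients lengthens the estimate even if the drug does nothing. The comparison is with a fixed historical median, so nothing offsets this.

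**Working it through.** **Inputs.** From Section 9.1: null median 1.7 months, exponential model, one-sided 10% level, N = 21. From Section 5.6.1: at most 25 enrolled, so at most 25 − 21 = 4 replacements. The second dose is due at day 14 (Section 6.1) and the first scheduled scan at week 8 (Section 7.3.1). The shares of failures lost are assumptions, because the documents give none.

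**Step 1: the plan's own figure.** Table 5 rejects on a lower tail ("Reject H0 if Theta-hat ≤ ThetaC") and prints power 0.90396 for N = 21 at 10%. If T is exponential, 2 × (number of events) × (true hazard) ÷ (estimated hazard) is chi-square with 42 df when all 21 fail. For the table's lower-tail rule with theta values 0.408 and 0.231, power = P(chi-square(42) ≤ 30.77 × 0.408/0.231 = 54.34) = 0.904, which matches. These values are ln2/1.7 and ln2/3, so Table 5 holds hazards under a mean-life label. The text's 4-month alternative differs from the 3 months implied here. That is a separate matter and does not affect the null calculations below.

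**Step 2: early events under the null.** Mean = 1.7/ln2 = 2.453 months. Day 14 = 14/30.4375 = 0.460 months; week 8 = 56/30.4375 = 1.840 months.

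- P(event before day 14) = 1 − exp(−0.460/2.453) = 0.171
- P(event before week 8) = 1 − exp(−1.840/2.453) = 0.528

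**Step 3: two decision rules.**

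- *Exact 10% test:* reject if mean PFS ≥ 2.453 × 54.09/42 = 3.159 months.
- *Table 5 cut-off on the hazard:* 0.4077 × 30.77/42 = 0.2987 (printed 0.3). Reject if the estimated hazard is at or below this, that is, if mean PFS ≥ 1/0.2987 = 3.348 months. Its type I error with no loss is P(chi-square(42) ≥ 42 × 3.348/2.453) = 0.058.

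**Step 4: type I error with loss and replacement.** Simulation under the null, 1,000,000 trials per case, at most 25 enrolled, first 21 evaluable analysed. Only 0.75% of PFS times exceed 12 months under the null, so administrative censoring is ignored.

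| Assumed loss | Exact 10% test | Table 5 cut-off |
|---|---|---|
| None | 0.100 | 0.058 |
| Lenient: 2%, 5%, 10% of all events before week 8 | 0.106, 0.114, 0.131 | 0.061, 0.067, 0.078 |
| Strict: 10%, 25%, 50% of events before day 14 | 0.112, 0.131, 0.173 | 0.065, 0.078, 0.106 |

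Under the strict reading, later undocumented failures would add to the last row.

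**Step 5: exclusions in the other direction.** Section 9.2.2 also drops patients who stop after one dose while event-free. If 5% or 10% of patients event-free at day 14 are dropped, the exact test falls to 0.095 or 0.088. Combined with loss of 10% of events before day 14, it is about 0.105 or 0.100. Dropout unrelated to outcome (2% to 10%) leaves both rules unchanged.

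**The case against.** **The exclusion is inferred.** Section 9.2.2 says who is replaced, not that replaced patients leave the PFS analysis, and its wording about response could describe a response set. Sections 2.1 and 9.3 place no evaluability limit on death or new therapy. This stands as a limit on the claim: a reader might infer that the plan specifies a biased analysis, but it only implies one. Even so, the sole efficacy set and the shared figure of 21 leave no other natural reading, and an unnamed set can be chosen after the data are seen.

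**The lost group may be small.** Entry requires life expectancy over 3 months, the first scheduled scan is at week 8, and "radiological tumor assessments will be conducted whenever disease progression is suspected". Few events before day 14 would be recorded, and many early progressions would be documented. This stands too. It weighs against the larger strict-reading shares, and more so against the extreme case of losing every event before day 14 (0.30, or 0.20 with the Table 5 cut-off).

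**The direction is not fixed.** A reader might infer that the Section 9.2.2 set can only favour the drug. That is true of the dropped failures but not of the whole set, as Step 5 shows.

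**The rules are reconstructions.** The plan states no test in Section 9.3. Under the cut-off that reproduces Table 5, only the 50% case in the table exceeds 10%. The inflation relative to no loss remains under both rules.

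**Conclusion.** The gap is real: the primary PFS set is not named, and the implied one removes some early failures because of their outcome under either reading of Section 9.2.2. For that part of the rule, type I error rises from 0.10 to about 0.11 to 0.13 (lenient) or 0.11 to 0.17 (strict) with an exact 10% test. With the Table 5 cut-off it rises from 0.058 to about 0.06 to 0.08 or 0.065 to 0.106.

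These sizes rest on assumed loss rates, the exponential model and the inference that Section 9.2.2 governs PFS. The documents do not support saying that the error must exceed 10%: opposite exclusions can cancel modest losses, and the cut-off matters. The cap of 25 limits replacements to four but does not limit how many patients are excluded. The net effect is likely, not certain, to favour the drug. Severity: should be fixed.

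**What to change.** - **Sections 9.2.2 and 9.3:** make the primary PFS set all patients who received at least one dose, counted from the first dose as in Section 2.1, with no replacement for efficacy.
- **Section 9.3:** censor treated patients without a PFS event at their last disease assessment, or at first dose if there is none. Base the exponential estimate on events over total follow-up. With censoring, the 42-df reference in Step 1 is no longer exact, so the test should be stated on this basis.
- **Sections 5.6.1 and 9.1:** state one number to be treated and analyse every patient treated. Twenty-one keeps the N of Section 9.1 and lies within the maximum of 25.
- **Section 9.4:** name the same set for OS.
- **Section 9.2.2:** keep the evaluable set as a sensitivity analysis, reworded so that the 'and/or' has one reading.

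The cost is wording only, with no patients beyond the present maximum. Reported PFS may be slightly less favourable.
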